5.6.2. Sensitivity Analysis

As sensitivity analysis for [T1] (primary), [T2], [T3] (key secondary), and MBS, following method will be conducted:

- The same analysis will be conducted based on ITT and PPS
- “non-responder” patients due to missing data (post baseline) will be excluded from (Reference Section [5.4.1](#)) mITT population

In addition, [T1] [T3] analysis will be conducted for patients who are in mITT and who have not vomited up to 2 hours. That is, eliminate patients who recorded vomiting at least once between 0 hour to 2 hours (inclusive), recorded in the eDiary.

In addition, as sensitivity analysis for [T1], separate subgroup models specified below will be fitted:

- [1] Previous triptan response (none + poor (0-1), good (2-3))
- [2] Baseline disability severity ('need complete bed rest', the others)
- [3] Baseline headache severity (moderate or severe)
- [4] Baseline associate symptom (with/without nausea)
- [5] Menstrual period (-2d before cycle to total 5 days)
- [6] Body weight (continuous variable)
- [7] Age (continuous variable)
- [8] Gender
- [9] Baseline migraine attacks (<=5 attacks per month, > 5 attacks per month)
- [10] Time of dose relative to onset of migraine (dosing time <= 1 hour, dosing time > 1 hour)
- [11] Duration of migraine history (<=median, > median)

The definition of [1] and [5] are the same as the one specified in Section [5.8](#).

The model term include treatment, baseline usage of preventive medications to reduce the frequency of migraine (Yes/No), subgroup, and treatment-by-subgroup interaction.

The response rate for each arm, along with 95% confidence interval, will be estimated based on LSMeans.

5.6.3. Details of Efficacy Analyses

Table LAIH. 5.3 is the list of primary/ key secondary/ other secondary/ exploratory analysis with each analysis population, timeframe and analysis method.

Table LAIH. 5.3 Primary, Key Secondary, Other Secondary and Exploratory Efficacy Variables and Analysis Methods

ID	Type	efficacy variables	POP	Timeframe	Analysis
1	PRIM /2 ND	Headache Pain Free	mITT/ ITT/ PPS	up to 48h	LOGISTIC
2	2KEY	Pain Free Trend Test	mITT/ ITT/ PPS	2h	CA
3	2KEY /2ND	Headache Pain Relief	mITT/ ITT/ PPS	up to 48h	LOGISTIC
4	2 ND	MBS-Free	mITT/ ITT/ PPS	up to 48h	LOGISTIC
5	2 ND	Migraine Symptoms Present at Assessment Times (Nausea, Phonophobia, Photophobia, Vomiting)	ITT	up to 48h	LOGISTIC
6	OTH	MBS-Free by Chosen Symptom: (Nausea, Phonophobia, Photophobia)	ITT	up to 48h	LOGISTIC
7	2 ND	Time to Headache Pain Free Through 48 Hours Post-Dose	ITT	up to 48h	KM
8	2 ND	Time to Headache Pain Relief Through 48 Hours Post-Dose	ITT	up to 48h	KM
9	2 ND	Time to MBS-Free Through 48 Hours Post-Dose	ITT	up to 48h	KM
10	OTH	Time to MBS-Free by Chosen Symptom Through 48 Hours Post-Dose: (Nausea, Phonophobia, Photophobia)	ITT	up to 48h	KM
11	2 ND	Disability	ITT	0.5h/1h/2h/24h	LOGISTIC

12	OTH	Incidence of Rescue or Recurrence Medication Use	ITT	[0h-2h]/ [2h-24h]/ [24h-48h]	LOGISTIC
13	OTH	Incidence of Headache Recurrence Through 24/48 Hours Post-Dose	ITT	2h< recurrence <=24h 2h< recurrence <=48h	LOGISTIC
14	2 ND	PGI-C	ITT	2h/24h	LOGISTIC
15	2 ND	Sustained Pain Free at 24 Hours and 48 Hours	ITT	24h/48h	LOGISTIC
16	2 ND	Time to No Disability Through 24 Hours	ITT	up to 24h	KM
17	OTH	Summary of Symptom-Free at Assessment Times (Nausea, Phonophobia, Photophobia, Vomiting)	ITT	up to 48h	LOGISTIC
18	OTH	Total Migraine Freedom	ITT	up to 48h	LOGISTIC
19	OTH	Modified Sustained Pain Free at 24 Hours and 48 Hours	ITT	24h/48h	LOGISTIC
20	OTH	Time to Meaningful Pain Relief Through 48 Hours	ITT	up to 48h (including 6h/8h)	KM
21	OTH	Time to Pain Free Through 48 Hours	ITT	up to 48h (including 6h/8h)	KM
22	2 ND	Change from Baseline of EQ-5D-5L in Index Score	ITT	24h	ANOVA
23	2 ND	Change From Baseline of EQ-5D-5L in Visual Analog Scale	ITT	24h	ANOVA
24	2 ND	HRQoL Measured by MQoLQ in 5 Domains	ITT	24h	ANOVA
25	2 ND	Treatment Satisfaction	ITT	48h	CMH

Abbreviations: 2KEY= key secondary analysis; 2ND= other secondary analysis; ANOVA= Analysis of Variance; CA= Cochran-Armitage trend test; CMH= Cochran-Mantel-Haenszel test; EQ-5D-5L = EuroQol 5-dimension 5-level scale; h= hour; HRQoL = Health-Related Quality of Life; ITT= intent-to-treat population ; KM= Kaplan-Meier analysis; LOGISTIC= logistic regression; MBS = the most bothersome symptom; MQoLQ = Migraine Quality of Life Questionnaire; mITT= modified intent-to-treat population; NA= not applicable (descriptive statistics is used); OTH= exploratory analysis; PGI-C = Patient Global Impression of Change; PPS= per protocol set population; PRIM= primary analysis

Definition of analysis used in [Table LAIH. 5.3](#) are listed below:

Pain Free

It is defined as reduction in headache severity from moderate (2) or severe (3) at baseline to none (0) at indicated assessment time.

Pain Relief

It is definition as reduction in headache severity from moderate (2) or severe (3) at baseline to mild (1) or none (0).

MBS-Free

MBS-free is defined as the absence of the associated symptom of migraine (either nausea, phonophobia, or photophobia) at the indicated assessment time that was identified pre-dose as the most bothersome symptom. Subjects who record that no symptoms were present at time of dose are excluded from the MBS analysis.

Migraine Symptoms Present at Assessment Times (Nausea, Phonophobia, Photophobia, Vomiting)

This is 4 separate analysis of Nausea, Phonophobia, Photophobia, Vomiting, regardless of corresponding baseline values.

MBS-Free by Chosen Symptom: (Nausea, Phonophobia, Photophobia)

This is 3 separate subgroup analysis of MBS. For example, the nausea analysis is based on those who chose “nausea” as the most bothersome symptom at baseline.

Time to Headache Pain Free Through 48 Hours Post-Dose

It is defined as a reduction in headache severity to pain free at any assessment time for the first time through 48 hours after the dose.

Time to Headache Pain Relief Through 48 Hours Post-Dose

It is defined as a reduction in headache severity to pain relief at any assessment time for the first time through 48 hours after the dose.

Time to MBS-Free Through 48 Hours Post-Dose

It is defined as the absence of the associated symptom of migraine, (either nausea, phonophobia, or photophobia) that was identified pre-dose as the most bothersome symptom, at any assessment time for the first time through 48 hours after the dose.

Time to MBS-Free by Chosen Symptom Through 48 Hours Post-Dose: (Nausea, Phonophobia, Photophobia)

This is 3 separate subgroup analysis of “Time to MBS Free Through 48 Hours Post-Dose”. For example, the nausea analysis is based on those who chose “nausea” as the most bothersome symptom at baseline.

Disability

Disability is measured on a four-point scale: not at all (0); mild interference (1); marked interference (2); and need complete bed rest (3). Proportion of patients with score = 0 for each group at each post baseline time point is analyzed. Note that patients with 0 severity at baseline will be excluded from the analysis. In addition, frequency of each category will be summarized.

Incidence of Rescue or Recurrence Medication Use

The analysis is conducted for 3 time frames, depending on rescue or recurrence medication dose time after the treatment intake: [0h<=dose<2h], [2h<=dose<24h], and [24h<=dose<=48h].

A subject is defined to have used rescue or recurrence medication if at least one medication is used during the time frame. Definitions of rescue/recurrence medication are in PROTOCOL Section 7.2.1.1.

Incidence of Headache Recurrence Through 24/48 Hours Post-Dose

It is defined that patients with pain-free at 2 hours post-dose becomes mild (1) or more before or at 24/48 hours post dose. We consider missing data as “non-recurrence” at each time point.

PGI-C

PGI-C is measured on a seven-point scale from “very much better” to “very much worse.” Responder is defined as top two categories, "very much better" and "much better". In addition, frequency of each category will be summarized.

Sustained Pain Free at 24 hours and 48 hours

Sustained Pain-Free is defined as experiencing headache pain-free at two hours after the dose and at the indicated assessment time, having not used any rescue/recurrence medications after the dose up to the assessment timing.

Time to No Disability Through 24 Hours

Disability is measured on a four-point scale: not at all (0); mild interference (1); marked interference (2); and need complete bed rest (3).

No Disability timing is defined as the first time when severity becomes 0. Note that patients with 0 severity at baseline will be excluded from the analysis.

Summary of Symptom-Free at Assessment Times (Nausea, Phonophobia, Photophobia, Vomiting)

This is 4 separate analysis of the symptom.

Total Migraine Freedom

If patients are pain free and are not experiencing any other migraine symptoms (i.e. nausea, photophobia, phonophobia, or vomiting), then they are total migraine free.

Modified Sustained Pain Free at 24 hours and 48 hours

Modified Sustained Pain-Free is defined as experiencing headache pain-free at two hours after the dose and no moderate or severe pain at the indicated assessment time, having not used any medications to treat migraine after the dose up to the assessment timing. Note that if a patient has missing evaluation at 24 hours, then he is excluded from the analysis instead of setting his response as nonresponder. The same is true at 48 hours evaluation.

Time to Meaningful Pain Relief Through 48 Hours

Meaningful Pain Relief timing is defined as the time when the corresponding eDiary question is answered as Yes.

Time to Pain Free Through 48 Hours

Pain Free timing is defined as the time when the corresponding eDiary question is answered as Yes.

Change from Baseline of EQ-5D-5L in Index Score

It is based on the EQ-5D Health Status Index Score. The Japan specific tariffs (Japanese population-based index value) for the EQ-5D Health Status Index Score is used. Change from baseline is based on Baseline (0 hour) and post-baseline (24 hours).

Change from Baseline of EQ-5D-5L in Visual Analog Scale

The change of EQ-5D-5L visual analog scale is based on Baseline (0 hour) and post-baseline (24 hours) from the onset of dosing.

HRQoL Measured by MQoLQ in 5 Domains

There are 5 domains in MQoLQ. Each domain will be analyzed separately: work functioning, social functioning, energy and vitality, feelings and concerns, and migraine symptoms. Each domain consists of 3 questions answered on a 7-point scale where 1 indicates maximum impairment and 7 indicating no impairment. A domain score is calculated by summing the responses to the 3 questions and the domain score ranges from 3 to 21. The response variable in this analysis is raw values at 24 hours.

Treatment Satisfaction

There are 4 questions. Each question will be analyzed separately. Distribution of responses and proportion of patients with agree or strongly agree will be summarized for each treatment group:

- the patient's level of satisfaction (ranging from extremely dissatisfied to extremely satisfied)
- their willingness to take this treatment again (ranging from strongly disagree to strongly agree)
- if they would they recommend this treatment to another patient (ranging from strongly disagree to strongly agree)
- their preference when comparing this treatment to the previous treatment ("prefer this treatment in comparison to my previous treatment" to "prefer my previous treatment in comparison to this treatment").

Regarding ratio of achieving Pain Free, Pain Relief, and MBS-free, MBS-Free by Chosen Symptom up to 2 hours for each arm, corresponding figures will be created based on mITT.

5.6.4. *Multiple Comparisons/Multiplicity*

In order to control for overall type I error (two-sided level of significance 0.05), the gate keeping method will be used for [T1], [T2] and [T3].

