EuroQol 5-Dimension 5-Level (EQ-5D-5L): EQ-5D-5L questionnaire is a widely used, generic questionnaire that assesses health status (The EuroQol Group 1990; Herdman et al. 2011). This is a patient-rated scale. The questionnaire consists of 2 parts. The first part assesses 5 dimensions (mobility, self-care, usual activities, pain/discomfort, and anxiety/depression) that have 5 possible levels of response (no problems, slight problems, moderate problems, severe problems, extreme problems). This part of the EQ-5D can be used to generate a health state index score, which is used to compute quality-adjusted life years for utilization in health economic analyses. The health state index score is calculated based on the responses to the 5 dimensions, providing a single value on a scale from less than 0 (where 0 is a health state

equivalent to death; negative values are valued as worse than death) to 1 (perfect health), with higher scores indicating better health utility. The second part of the questionnaire consists of a visual analog scale on which the patient rates their perceived health state from 0 (the worst health you can imagine) to 100 (the best health you can imagine). The EQ-5D-5L will be captured at Visit 2 and at 0 and 24 hours postdose of study drug.

Disability: Disability will be measured by determining the level of interference with normal activities with 4 response options including not at all; mild interference, marked interference; and need complete bed rest. This will be evaluated at 0 (pre dose), 0.5, 1, 2, and 24 hours postdose of study drug.

PGI-C: Patient global impression of change will be measured at 2 and 24 hours postdose of study drug with a 7-point scale ranging from very much better to very much worse.

Treatment Satisfaction: Treatment satisfaction will be evaluated at 48 hours postdose of the study drug by determining the patient's level of satisfaction (ranging from extremely dissatisfied to extremely satisfied); their willingness to take this treatment again (ranging from strongly disagree to strongly agree); if they would they recommend this treatment to another patient (ranging from strongly disagree to strongly agree) and their preference when comparing this treatment to the previous treatment ("prefer this treatment in comparison to my previous treatment" to "prefer my previous treatment in comparison to this treatment").

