5.2. Sample Size Determination

Approximately 1157 patients will be screened to achieve approximately 880 patients randomized, and approximately 624 patients with data for a migraine attack.

[Table LAIH. 5.1](#) illustrates the power calculation.

The power calculation is based on the results of the Study SPARTAN*. The primary endpoint (headache pain free at 2 hours postdose) results in SPARTAN were 21.3%, 28.6%, 31.4%, and 38.8% for placebo, lasmiditan 50 mg, lasmiditan 100 mg, and lasmiditan 200 mg, respectively, and the rates of headache pain relief at 2 hours postdose were 47.7%, 59.0%, 64.8%, and 65.0% for placebo, lasmiditan 50 mg, lasmiditan 100 mg, and lasmiditan 200 mg, respectively.

To ensure sufficient total statistical power for the primary and two key secondary analyses, the number of randomized patients will be set at 880. Considering 29% dropout rate, this sample size has 85.6% power. More specifically, the study will include:

- Number of screened patients = 1157.
- Number of randomized patients = 880 (= 1157*0.76, approximately 24% screen failure based on assumptions from LAIJ***), with [placebo:lasmiditan 50 mg:lasmiditan 100 mg:lasmiditan 200 mg] = 268:114:268:230 (7:3:7:6 ratio) for the attack.
- Number of patients who have a migraine attack = 624 (= 880*0.71, approximately 29% of patients would not dose to treat a migraine attack during the 8 week period based on SPARTAN/SAMURAI**), with [placebo:lasmiditan 50 mg:lasmiditan 100 mg:lasmiditan 200 mg] = 190:81:190:163 (7:3:7:6 ratio).

Note*: SPARTAN is the Study COL MIG-302/H8H-MC-LAHK.

Note**: SAMURAI is the Study COL MIG-301/H8H-MC-LAHJ.

Note***: LAIJ is the Study H8H-MC-LAIJ.

Note: The power is calculated based on simulation. In the simulation, the correlation between pain free and pain relief was assumed to be zero which would result in a conservative power.

Table LAIH. 5.1 Study Power Calculation

	Arm	N
Arm and number of patients	PLA	190
	LY50	81
	LY100	190
	LY200	163
	Total	624
Power	Primary [T1] : PLA vs LY200 = 93.6% (2 sided, alpha = 0.05) Key secondary [T2]: CA (PLA,LY50,LY100,LY200) = 94.9% (2 sided, alpha = 0.05) Key secondary [T3]: PLA vs LY100 = 91.2% (2 sided, alpha = 0.05) Total (primary and two key secondaries) = 85.6%	
Primary endpoint/Key secondary endpoints	[T1] and [T2]: Pain free at 2 hours postdose [T3]: Pain relief at 2 hours postdose	

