5.4. General Statistical Considerations

Statistical analysis of this study will be the responsibility of Lilly or its designee.

In general, we will use the following statistical methods unless otherwise specified. For detailed definitions of [T1] (primary objectives), [T2] and [T3] (2 key secondary objectives), see Section [5.6.1](#):

- For efficacy analyses based on proportion, the logistic regression used in [T1] will be applied. The model term includes treatment and baseline usage of preventive medications to reduce the frequency of migraine (Yes/No).
- When treatment group (PLA, LY50, LY100, LY200) is in a statistical model, it will be regarded as a categorical variable.
- For analysis based on continuous variable (change from baseline), if analysis of variance (ANOVA) is used then its covariate includes treatment and baseline usage of preventive medications to reduce the frequency of migraine (Yes/No). LSMeans will be used for estimation.
- For safety analyses and demographics, only descriptive statistics will be presented, and no statistical test will be conducted.
- Statistical tests will be conducted at a 2-sided significance level of 0.05. The 95% confidence interval will be presented if appropriate.
- No multiplicity adjustment for multiple tests (between the arms for the same efficacy objective, nor between the different objectives for the same arms) will be made except primary and two key secondary analyses ([T1], [T2], and [T3]).
- Analyses will be reported by 4 treatment groups (PLA, LY50, LY100, LY200) in general.
- Frequency tables such as those for AE or TEAEs will be sorted by LY_ALL, in decreasing frequency.
- For safety, 5 treatment groups (PLA, LY50, LY100, LY200, LY_ALL) will be displayed.
- For demographics, 6 treatment groups (PLA, LY50, LY100, LY200, LY_ALL, Overall) will be displayed. Here “Overall” means all combined arms (PLA + LY_ALL).
- For efficacy analyses based on proportions, odds ratio along with 95 % confidence interval will be calculated at 2 hours post-dose time point (each treatment vs. placebo).

- When Cochran-Mantel-Haenszel test is used for a multi-category response, baseline usage of preventive medications to reduce the frequency of migraine (Yes/No) is used for stratification (each treatment vs. placebo).

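### The 'no disability' model (ID 11) leaves out the pre-dose disability level the eDiary already records; adding it is a cheap gain in precision, probably a small one

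*SAP*

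**What the plan says.** No disability at 2 hours is an other-secondary endpoint for all three doses (Protocol Section 4; SAP Table LAIH. 4.1). In SAP Table LAIH. 5.3 it is ID 11: logistic regression in the ITT population at 0.5, 1, 2 and 24 hours. SAP 5.6.3 defines the response: "Proportion of patients with score = 0 for each group at each post baseline time point is analyzed". Patients scoring 0 before dosing are left out and every category is tabulated, but the entry names no covariate. The model terms therefore come from SAP 5.4: "The model term includes treatment and baseline usage of preventive medications to reduce the frequency of migraine (Yes/No".

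The pre-dose value exists. Protocol 9.1.2 says of the disability item: "This will be evaluated at 0 (pre dose), 0.5, 1, 2, and 24 hours postdose of study drug". The eDiary appendices of both documents agree.

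The SAP uses pre-dose disability in two other places:
- SAP 5.6.2, for pain freedom [T1] only, as model "2] Baseline disability severity ('need complete bed rest', the others".
- SAP 5.8, as subgroup SUB5 in the mITT population, again bed rest against the rest. It covers disability at 2 hours within each subgroup and in an interaction model.

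Protocol 10.3.3.1 leaves any further covariates to the SAP.

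**The concern.** The omitted variable is the baseline value of the outcome itself. A patient with mild interference is one step from score 0, and a patient needing complete bed rest is three steps away. If that distance matters, part of the outcome variation is predictable before dosing, and a model without the term compares the arms against more noise than it needs to. Neither existing use of the variable fills the gap: one concerns pain freedom, and the other is a two-level subgroup analysis that merges mild with marked. At stake is some precision for three dose comparisons at four time points, and adjustment for any chance imbalance in pre-dose disability. Randomisation is stratified on preventive use alone (Protocol 7.2).

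**Working it through.** **1. Inputs from the documents.** Level: "Statistical tests will be conducted at a 2-sided significance level of 0.05". Planned arms (placebo, 50, 100, 200 mg): "190:81:190:163 (7:3:7:6 ratio". Pain-free rates: "results in SPARTAN were 21.3%, 28.6%, 31.4%, and 38.8% for placebo" and the three doses in order. Pain-relief rates: "47.7%, 59.0%, 64.8%, and 65.0% for placebo" and the doses likewise (all SAP 5.2).

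**2. Reproducing the plan's own power.** Power = Φ[(Δ − 1.96·SE0)/SE1], with SE0 pooled and SE1 unpooled.
- T1: Δ = 0.388 − 0.213 = 0.175; pooled rate (190 × 0.213 + 163 × 0.388)/353 = 0.294; SE0 = 0.0486; SE1 = 0.0484. Power = Φ(1.65) = 95.0% (stated 93.6%).
- T3: Δ = 0.648 − 0.477 = 0.171; SE0 = 0.0509; SE1 = 0.0501. Power = Φ(1.42) = 92.2% (stated 91.2%).
- By simulation, with pain freedom and pain relief uncorrelated as the SAP assumes, T2 is 94.9% (stated 94.9%) and all three together 87.0% (stated 85.6%).

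The stated figures reproduce within 2 points. No power is stated for disability.

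**3. Assumptions for disability (none is in the documents).**
- No disability at 2 hours, placebo against 200 mg: 20 v 32%, 25 v 38%, 35 v 48%.
- Pre-dose mix mild/marked/bed rest: 25/50/25% and 35/45/20%.
- logit P(score 0) = α + τ(arm) + β·level, with level 0, 1, 2 and exp(β) the odds ratio per worse level. α and τ are set so that the overall rates in both arms stay fixed as β changes.
- Arms of 190/81/190/163. These are the planned mITT numbers; ID 11 uses ITT without score-0 patients, so the true numbers will differ.
- 6,000 trials per scenario. Each is fitted with treatment alone and with treatment plus the three-level pre-dose score, using a two-sided Wald test of 200 mg against placebo. Preventive use is left out of both fits.

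**4. Results.** Simulated power without the term is 68 to 76%. The ranges below span the six combinations of rates and mix.

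| Odds ratio per worse level | Gain in power (points) | Relative efficiency |
|---|---|---|
| 1.0 | −0.4 to +0.5 (noise) | 1.00 |
| 0.8 | +0.2 to +1.0 | 1.00 to 1.01 |
| 0.7 | +0.2 to +1.4 | 1.01 to 1.02 |
| 0.6 | +0.6 to +1.7 | 1.02 to 1.03 |
| 0.5 | +1.5 to +3.2 | 1.04 to 1.06 |
| 0.4 | +2.5 to +4.6 | 1.07 to 1.10 |
| 0.3 | +5.0 to +7.1 | 1.12 to 1.16 |

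**5. Hand check.** Adjusted power ≈ Φ(√RE × (1.96 + z) − 1.96), where z is the normal quantile of the unadjusted power. For 25 v 38%, mix 25/50/25% and odds ratio 0.5 (placebo rates by level 39/24/14%), unadjusted power is 74.7%, so z = 0.665. With RE = 1.050: 1.025 × 2.625 − 1.96 = 0.73, and Φ = 76.7% (simulated 76.5%). An RE of 1.05 is worth about 0.05 × 353 ≈ 18 patients over the two arms.

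**6. A more extreme set of assumptions.** Mix 25/45/30%, conditional odds ratio 1.9 for 200 mg, 190 against 163 patients, 3,000 trials each.

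| Placebo rates mild/marked/bed rest | Odds ratio at each step | Power without → with |
|---|---|---|
| 35/25/18% | 0.62, 0.66 | 77% → 79% |
| 50/22/10% | 0.28, 0.39 | 68% → 73% |
| 65/18/5% | 0.12, 0.24 | 50% → 64% |

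In the last row the odds of response for mild against bed rest differ by (0.65/0.35)/(0.05/0.95) ≈ 35-fold. Because the conditional odds ratio is held fixed, the overall 200 mg rate also falls, from 38.9% in the first row to 35.5% in the last, against about 25% on placebo. Part of the drop in unadjusted power is therefore a smaller marginal effect.

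**The case against.** The plan makes no error here. The endpoint is a proportion per arm. Treatment plus the factor used for stratification, applied alike to the proportion analyses, is a defensible prespecified model, and the protocol left further covariates optional. ID 11 lies outside the gatekeeping and has no multiplicity control (SAP 5.4, 5.6.1). SUB5 would already show whether the 2-hour result differs by bed rest. All of this stands. It limits the weight of the point but does not supply an adjusted overall comparison.

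Three stronger readings are tempting but not supported:
- **That the planned model treats all pre-dose levels as equally likely to respond, or is biased.** A model without the term averages over the levels. Under randomisation its test is valid.
- **That the smallest arm, 50 mg, loses most.** Protocol 5.4 says 50 mg showed the least efficacy. With 190 against 81 patients and an assumed conditional odds ratio of 1.4, the gains in the three scenarios of step 6 are about 1, 2 and 4 points. If 50 mg is given the same odds ratio as 200 mg (1.9), the gains are 1.0, 6.5 and 10.7 points, against 0.6, 5.1 and 13.6 for 200 mg in matching runs. There is no general pattern.
- **That about 14 points of power are at stake (50% to 64%).** That needs the 35-fold contrast above, which nothing in the documents supports. It is an extreme upper bound.

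Adding the term everywhere would also have a cost: small subgroups, and early time points where few patients may have reached score 0, could give sparse cells.

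**Conclusion.** The point holds as an optional improvement in efficiency. ID 11 omits an already collected baseline value of its own outcome. If that value is prognostic, the planned comparison is somewhat less precise than it could be; if it is not, nothing measurable is lost by including it. A gain of about 1 to 3 points, or 2 to 6% in sample-size terms, corresponds to odds ratios of 0.5 to 0.6 per level. Gains of 5 to 7 points need about 0.3. These sizes depend on assumed response rates, pre-dose mix and prognostic strength, so the documents cannot establish the actual gain. The validity of the planned test, the stated power for T1 to T3 and the confirmatory conclusions are untouched.

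**What to change.** Before unblinding, amend SAP 5.6.3 for ID 11:
- Add hour-0 disability (mild, marked, complete bed rest) as a categorical covariate to the main model, with 2 hours as the main time point. Keep the exclusion of score 0.
- At 0.5, 1 and 24 hours include the term where cell counts allow, merging levels if they are sparse. State that rule in advance.
- Label the odds ratio as conditional on pre-dose disability, and keep the current model as a sensitivity analysis.
- Leave the subgroup models in Table LAIH. 5.6 as planned.

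The cost is one model term and a few sentences, with no new data. The downsides are that the odds ratio will not be directly comparable with those of the other binary endpoints, and that sparse cells are possible at early time points.
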